20.3 GENERAL STATISTICS

Descriptive statistics will typically include sample size (N), mean, standard deviation (SD), minimum (Min) and maximum (Max) as appropriate for continuous variables. For dichotomous variables, the frequency and proportion will be reported and McNemar's test will be applied. For continuous variables, statistical tests (paired t-test) assuming normality will generally be used. For ordinal categorical data, the frequency and proportion will be reported and Wilcoxon signed-rank test will generally be applied.

20.4 INTERIM REPORTS

Due to the short duration of this study, no interim study reports are anticipated. However, should a progress report be required for regulatory purposes (e.g., FDA progress report), all masking will be maintained. If any interim analyses need be performed for product registration or release in other countries that require unmasking and reporting of effectiveness outcomes, they will be conducted by an independent body to avoid bias. Interim reports will not be disseminated to investigators/site personnel or to AMO staff working directly with study sites and monitoring incoming data.

20.5 SAMPLE SIZE CALCULATIONS

Cumulative IOP spikes are defined as an IOP of 30 mm Hg or greater at any visit. The percentage of eyes with IOP spikes will be assumed to be 30% (15798:2001(E), Annex D), and a correlation of 0.5 (medium strength). Using a one-sided, McNemar test and assuming an alpha of 0.025, power = 0.80, and a minimum detectable difference of $\delta=0.10$ yields a sample size of $n=195$ eyes per group. Adding 20% for lost-to-follow-up and screen failures yields a sample size of up to 241 enrolled subjects with the intent to approximately 230 subjects to ensure 200 evaluable subjects.

Assuming a 1-sided, non-inferiority, paired t-test with $\alpha=0.025$, a common standard deviation of 305 cells⁴, and a correlation of 0.50 (medium strength), a sample of $n=195$ subjects (390 eyes) provides over 99% power to detect a minimum clinically significant decrease in mean Endothelial Cell Count (ECC) of at least $\delta =125$ cells. This corresponds to a 5% decrease using a standard deviation of 12% from a baseline ECC of 2500 cells.

Since the sample size required to detect a minimum clinically significant effect for IOP spikes also provides over 99% power to detect a minimum clinically significant effect for ECC loss, the sample size for the study will be based on the number calculated for IOP spikes. Therefore, the sample size required is 195 subjects. Adding 20% for lost-to-follow-up and screen failures yields a sample size of 241 subjects (482 eyes).

APPENDIX A SUMMARY OF PROCEDURES REQUIRED AT EACH VISIT

Examination	Preop Both Eyes	Op 1 1 st Eye	6 hrs 1 st Eye	1 day 1 st Eye	1 wk 1 st Eye	Op 2 2 nd Eye	6 hrs 1 st Eye	1 day 2 nd Eye	1 wk 2 nd Eye	1 mo Both Eyes	3 mo Both Eyes
Ocular history, inclusion/exclusion criteria	X										
Informed consent	X										
Potential visual acuity	X										
Randomization		X									
Lens power/serial number/operative procedures		X				X					
UCDVA – photopic, monocular (Snellen)				X				X			
BCDVA - photopic, monocular (Snellen)	X				X				X	X	X
Intraocular pressure (Goldmann)	X		X	X	X		X	X	X	X	X
Endothelial cell count	X										X
Biomicroscopic slit-lamp exam ^a	X		X	X	X		X	X	X	X	X
Dilated fundus exam	X										X ^b
Adverse events		X	X	X	X	X	X	X	X	X	X
Ocular medications	X	X	X	X	X	X	X	X	X	X	X
Ocular/visual symptoms (non-directed)				X	X			X	X	X	X

^a Includes determination of medical and lens findings/complications

^b Only if medically indicated

APPENDIX B EQUIPMENT LIST

The following equipment will be supplied to an investigative site for the duration of the study provided that the site does not already have such equipment available for use. This equipment loan will be documented in the Clinical Trial Agreement, which indicates that the equipment is to be returned to Abbott Medical Optics at the completion of the study.

- Konan Specular Microscope (if necessary)
- Aegis Refrigerator and Sensor

APPENDIX C ENDOTHELIAL CELL COUNTS

Endothelial cell counts (ECC) will be performed with a Konan non-contact specular microscope capable of capturing ECC images electronically at both the preoperative and the 3-month visits. Three acceptable images should be taken at each of these two visits. If possible; throughout the study the same technician/photographer at each site should take all the images.

A Konan technician will work directly with each study site to ensure proper calibration of the specular microscope and train/retrain appropriate site staff on the proper technique for capturing quality images. Prior to study initiation, each site must submit two sample images to the central reading center (EyeKor, Inc.) to ensure good quality images with clearly defined endothelial cells.

For preoperative subject qualification, the study technician should record the lowest of the three ECC values on the case report form for each eye. If the lowest value for either eye is below 1800 cells/mm², the subject should not be enrolled.

Throughout the course of the study, sites are to send all study images directly to the central reading center for analysis. The preoperative and three-month postoperative images will be sent to EyeKor using EXCELSIOR software without any indication of the treatment group

Analyses will be performed using the mean of the three images for each subject at each time point.

APPENDIX D SLIT-LAMP EXAM RATINGS

A. Ratings of Aqueous Cells and Flare

For consistency across study sites, the SUN (Standardization of Uveitis Nomenclature) Working Group Grading Scheme is to be used for grading of anterior chamber cells and flare as reported in: Standardization of uveitis nomenclature for reporting clinical data. Results of the first international workshop; The standardization of uveitis nomenclature (SUN) working group, Am J Ophthalmol 2005;140:509-516.

CELLS

Grade	Cells in Field (Field is a 1x1 mm slit beam)
0	<1
0.5+	1 - 5
1+	6 - 15
2+	16 - 25
3+	26 - 50
4+	>50

FLARE

Grade	Description
0	None
1+	Faint
2+	Moderate (iris and lens details clear)
3+	Marked (iris and lens details hazy)
4+	Intense (fibrin or plastic aqueous)

B. Ratings of Corneal Edema

Corneal edema should be classified according to the haziness of the epithelium, the number of microcysts observed, and the clouding of the stroma.

Amount	Grade	Description
None	0	Normal transparency: a. No epithelial or sub-epithelial haziness b. No microcysts c. No stromal cloudiness
Trace	+1	a. Barely discernable localized epithelial or sub-epithelial haziness, and/or b. 1 to 20 microcysts, and/or c. Barely discernable localized stromal cloudiness
Mild	+2	a. Faint but definite localized or generalized epithelial, sub-epithelial or stromal haziness/cloudiness, and/or b. 21-50 microcysts
Moderate	+3	a. Significant localized or generalized epithelial, sub-epithelial or stromal haziness/cloudiness and/or b. 51-100 microcysts
Severe	+4	a. Definite widespread epithelial or stromal cloudiness, giving dull glass appearance to cornea or numerous coalescent bullae (please note the number and location of bullae), and/or b. >100 microcysts or bullae, and/or c. Numerous striae (please note the number and location of striae or folds)

C. Posterior Capsule Striae Grading Scale

The following five-point grading scale is to be used for rating striae in the posterior capsule:

Amount	Grade	Description
None	0	None
Trace	+1	One detectable, barely noticeable striae
Mild	+2	One or two prominent striae
Moderate	+3	Three or more prominent striae, but visibility of retina is not impacted
Severe	+4	Three or more prominent striae affecting visualization of retina

D. Posterior Capsule Opacification Grading Scale

Below is the five-point grading scale to be used for PCO determination:

Amount	Grade	Description
None	0	Normal posterior capsule with no area of opacity. Red reflex bright.
Trace	+1	Some loss of transparency involving the posterior capsule. Red reflex fairly bright
Mild	+2	Mild loss of transparency with cloudiness extending through most of the posterior capsule. There may be a few Elschnig's pearls in the posterior capsule. Red reflex mildly diminished.
Moderate	+3	Moderate loss of transparency with difficulty visualizing the retina. There may be multiple Elschnig's pearls in the posterior capsule. Red reflex markedly diminished.
Severe	+4	Posterior capsule very opaque with inability to view the retina. The posterior capsule may have confluent Elschnig's pearls and fibrous scarring. Red reflex barely visible.

APPENDIX E ADVERSE EVENT AND COMPLAINT REPORTING INSTRUCTIONS

All adverse events and complaints related to using AMO products must be reported to AMO.

ALL ADVERSE EVENTS AND COMPLAINTS:

For events that are not considered serious or related to the study device:

1. Record the event and/or complaint on the case report form that corresponds to the visit during which awareness of the event occurred. Additionally, a complaint may be reported via a telephone call to AMO.
2. Send the completed case report form to AMO in a timely manner

SERIOUS ADVERSE EVENTS OR DEVICE DEFICIENCIES THAT MAY HAVE LED TO A SERIOUS EVENT

In the event of a serious event (i.e., life- or sight-threatening incident) whether or not related to the device, or a device deficiency that may have led to a serious event, the investigator shall:

1. Notify AMO immediately (no more than 48 hours after learning of the event) as follows:
 - a. Contact the following AMO personnel by phone and/or email:
[name]
[contact]
[contact]

[name]
[contact]
Office: [contact]
[contact]
 - b. Submit an SAE/ADE Detailed Page to AMO

NON-SERIOUS, DEVICE-RELATED EVENTS:

For events that are not considered serious but are believed related to the study device (ADEs):

1. Complete an SAE/ADE Detailed Page
2. Ensure the data are submitted to AMO within a timely manner.

1 INTRODUCTION

This document summarizes the statistical methods to be implemented during the analysis of data for the bacterially-derived Healon5 ophthalmic viscosurgical device (OVD) VSCO-109-HLN5 study. This study will be a 3 month, prospective, multicenter, paired-eye, randomized, masked clinical trial. Subjects will be randomized to receive bacterially-derived Healon5 OVD in one eye and currently-available animal-derived Healon5 OVD in the other eye according to a centralized electronic randomization system. It is expected that there will be 200 evaluable subjects at the 3 month timeframe.

There are two primary endpoints for this study: cumulative rate of intraocular pressure (IOP) spikes 30 mmHg or greater postoperative and mean percent change of endothelial cell count (ECC) preoperatively vs. postoperatively at 3 month.

The secondary safety endpoints are rates of serious and/or device-related adverse events, distribution of the grade of inflammation, IOP spikes of 30 mmHg or greater at 6 hours, 1 day, 1 week, 1 month and 3 months postoperatively, and mean change in IOP from baseline.

Additional endpoints are optical/visual symptoms (non-directed), medical findings/adverse events (non-serious, non-device related), monocular best corrected distance visual acuity (BCDVA) 20/40 or better vs. ISO SPE rate, and uncorrected distance visual acuity (UCDVA).

2 ANALYSIS POPULATIONS

2.1 ANALYSIS POPULATIONS/HANDLING OF MISSING DATA

Four different populations will be presented for the primary endpoints (cumulative IOP spike, and mean percent ECC change): Intent-to-Treat (ITT), sensitivity analysis, safety population, and per-protocol population. The ITT population will be the primary analysis population for the primary endpoints and will include all subjects who were randomized and had surgeries using the test OVD in one eye and the control OVD in the other eye (i.e., paired OVDs were used). Sensitivity analysis will include all subjects who were randomized regardless of OVD use; i.e., include subject that had no study OVD, one study OVD or paired OVDs used. The safety population will include available subjects who had one or both study OVDs. The per-protocol population will include available subjects who had surgeries with paired OVDs, were evaluated within the proper study interval and were without clinically-relevant protocol deviations

For the secondary safety endpoints and other additional study endpoints, only data from the safety population will be presented.

INTENT-TO-TREAT ANALYSIS

The ITT population will include all subjects who were randomized and had surgeries using a test OVD in one eye and a control OVD in the other eye (i.e., paired OVDs). For randomized subjects who had study OVDs but did not have data available at a specific postoperative visit, (e.g. they missed a visit, were lost to follow-up), data will be imputed for the ITT analyses using a planned multiple imputation method. The planned imputation method is the MCMC full-data imputation as described in Little & Rubin¹. Data imputation and analysis will be performed using the MI and MIANALYZE procedures² in SAS®.

SENSITIVITY ANALYSIS

Sensitivity analysis will include all subjects who were randomized whether they had none, one OVD or both OVDs. For missing data in the sensitivity analysis, different imputation approaches (e.g. worst-case scenario, best-case scenario and tipping point) will be used. For the difference between eyes, a worst-case scenario will be performed with the worst difference score (that favoring the control the most) assigned to the missing data. For the best-case scenario, the difference score favoring the control OVD the most will be assigned to missing data. If more than 10 percent of randomized subjects have missing data at the primary analysis time point then a tipping point analysis will also be performed.

SAFETY (SF) ANALYSIS

The safety population will consist of all subjects who had any study OVD used and with data available at the time of analysis (i.e., no data imputation). For endpoint analyses using the safety population, if a subject receives only one study OVD then their data will be reported separately since they will not have any between eye difference values. However, if only one eye had a study OVD, then data for that eye will be included in reporting of adverse events and complications. Reporting of cumulative complications (occurring at any time postoperative) will include data from all eyes that had a study OVD.

PER-PROTOCOL (PP) ANALYSIS

The PP population will only include subjects who had surgeries with paired OVDs used, were evaluated within the proper study interval and were without clinically-relevant protocol deviations (deviations that could potentially impact the primary or secondary endpoints for either eye as determined prior to database lock). PP tables will include available data at the time of analysis with no data imputation performed.

Appendix I lists the analysis tables including the endpoints and the populations used to report the results.

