- Patient is pregnant, plans to become pregnant, is lactating or has another condition associated with the fluctuation of hormones that could lead to refractive changes
- Concurrent participation or participation within 45 days prior to preoperative visit in any other clinical trial

EVALUATION CRITERIA:

The purpose of this clinical study is to evaluate the safety and effectiveness of the non-animal-derived Healon5 OVD. The primary endpoints are cumulative rate of intraocular pressure (IOP) spikes of 30 mmHg or greater postoperatively and mean percent change of endothelial cell count (ECC) postoperatively vs preoperatively. The secondary safety endpoints are rates of serious and/or device-related adverse events, distribution of the grade of inflammation, IOP spikes of 30 mmHg or greater at 6 hours, 1 day, 1 week, 1 month and 3 months postoperatively, and mean change in IOP from baseline. Additional endpoints are other medical findings/adverse events (non-serious, non-device-related), monocular best corrected distance visual acuity (BCDVA) percent 20/40 or better vs. ISO SPE rates, optical/visual symptoms, and uncorrected distance visual acuity (UCDVA) at 1 day.

As this study is masked, an independent Data Safety Monitoring Board (DSMB) will monitor medical complications and adverse events that occur during the study.

DATA ANALYSIS:

For primary endpoints of cumulative IOP spike rate and mean percent ECC change, the primary analysis population will be an Intent-to-Treat (ITT) population. For missing data, data imputation will be performed using MCMC multiple imputation techniques¹. The safety population (SP) will be used for secondary safety endpoints and other supportive endpoints. Per-protocol and sensitivity analyses (e.g., worst-case, best-case and tipping-point analyses) will also be provided for the primary endpoints.

For cumulative IOP spike rate, comparison between OVD groups will be performed using a 1-sided, McNemar test of non-inferiority at an alpha of 0.025 and a non-inferiority margin of 0.10 (10%). For mean percent ECC change, comparison between OVD Groups will be performed using a 1-sided, paired t-test of non-inferiority at an alpha of 0.025 and a non-inferiority margin of 5%. If percent ECC change does not meet normality assumption, a non-parametric test will be performed to evaluate the non-inferiority of mean percent ECC change.

STUDY VISITS AND PROCEDURES:

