20.1 ANALYSIS POPULATION

For the primary endpoints of cumulative IOP rate and mean percent ECC change, the primary analysis population will be an Intent-to-Treat (ITT) population. The ITT population will include all subjects who were randomized and had surgeries using a test OVD in one eye and a control OVD in the other eye. For randomized subjects who received study OVDs but did not have data available at a specific postoperative visit

(i.e., missing postoperative data), data imputation will be performed using MCMC multiple imputation techniques¹. Per-protocol and sensitivity analyses (e.g., worst-case, best-case and tipping-point analysis) will also be provided for the primary IOP and ECC endpoints. Sensitivity analyses will include all randomized subjects whether a study OVD was used or not. The safety population (SP) will include available subjects who had one or both study OVDs with available data at the time of analysis (i.e., no data imputation). Only the safety population will be used for analyses of secondary safety endpoints and other endpoints. For the secondary safety endpoints, no multiplicity or imputation will be done since they are considered safety endpoints and are not intended for claims. Only safety population (SP) will be used for the secondary safety endpoints.

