8 SAMPLE SIZE CALCULATIONS

Cumulative IOP spikes are defined as an IOP of 30 mm Hg or greater at any visit. The percentage of eyes with IOP spikes will be assumed to be 30% (15798:2001(E), Annex D), and a correlation of 0.5 (medium strength). Using a one-sided, McNemar test and assuming an alpha of 0.025, power = 0.80, and a minimum detectable difference of $\delta=0.10$ yields a sample size of $n=195$ eyes per group. Adding 20% for lost-to-follow-up and screen failures yields a sample size of 241 subjects (482 eyes total with contralateral control).

Assuming a 1-sided, non-inferiority, paired t-test with $\alpha=0.025$, a common standard deviation of 305 cells⁵, and a correlation of 0.50 (medium strength), a sample of $n=195$ subjects (390 eyes) provides over 99% power to detect a minimum clinically significant decrease in mean Endothelial Cell Count (ECC) of at least $\delta =125$ cells. This corresponds to a 5% decrease using a standard deviation of 12% from a baseline ECC of 2500 cells.

Since the sample size required to detect a minimum clinically significant effect for IOP spikes also provides over 99% power to detect a minimum clinically significant effect for ECC loss, the sample size for the study will be based on the number calculated for IOP spikes. Therefore, the sample size required is 195 subjects. Adding 20% for lost-to-follow-up and screen failures yields a sample size of 241 subjects (482 eyes).

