APPENDIX I: TABLE LISTING

| | Test Eye | Control Eye | Comments/ Population |
|---|-----------------|--------------------|---------------------------------|
| ENROLLMENT/PREOP/OP | | | |
| Accountability/Enrollment | | | |
| No. of eyes by OVD model by investigational site | X | X | SF/PP/ITT/Sensitivity |
| Accountability table over time – (No of eyes will be reported for: available for analysis, missing data -discontinued, In interval (no form), missed visit, lost to follow-up, active | X | X | SF/PP/ITT |
| Out of interval subjects listing – No. of eyes | X | X | SF/PP/ITT |
| Demographics | | | |
| Demographic –Age in years (N, Mean, SD, Min., Max), age in groups (<60,60-69,70-79,>=80), race, ethnicity, sex, iris color | | | ITT/SF/PP (By Subject) |
| Age by Site (N, Mean, SD, Min. Max.) | | | SF (By Subject) |
| Other demographic data by site (race, ethnicity, sex) | | | SF (By Subject) |
| Preoperative Characteristics | | | |
| Visual Acuity: No. and percent of eyes for each category | X | X | SF |
| Potential Visual Acuity (≤20/40,>20/40) BCDVA (≤20/30, 20/40, 20/50-20/80, 20/100, >20/100) UCDVA (≤20/40, 20/50-20/80, 20/100, >20/100) | | | |
| Other Preop Items: No. and percent of eyes for each category | X | X | SF |
| Non-clinically significant pathology and/or Medical findings (by finding) | | | |
| Operative Data | | | |
| General Surgical Parameters: No. and percent with each response | X | X | SF |
| IOL model implanted (ZCB00, PCB00, ZKB00, ZLB00, ZMB00) Incision location (Superior, temporal, steep axis, other) Lens placement (Capsular bag, other) Type of Closure (Sutureless, suture) Any concerns/issue with AMO product as part of preparing, performing and/or completing the surgery? (Yes/No) Capsulotomy method (by type) Lens removal method (by method) | | | |
| Surgical Complications: No. and percent with each response | X | X | SF |
| Surgical complications (none, all items listed on CRF, other) Other surgical procedures (none, all items listed on CRF, other) | | | |

| | Test Eye | Control Eye | Comments/ Population |
|--|----------|-------------|-----------------------|
| PRIMARY EFFECTIVENESS ENDPOINTS | | | |
| Cumulative IOP 30mmHg spike rate (95% CI.) between OVD groups | X | X | ITT/Sensitivity/SF/PP |
| Cumulative IOP 30mmHG spike rate (No. and percent) by OVD groups | | | Sensitivity/SF/PP |

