| Mean difference between OVD groups in percent ECC change preoperatively vs. 3 months (N, Mean, SD, Median, Min., Max, 95% CI.) | X | X | ITT/Sensitivity/SF/PP |
| Mean percent change of ECC preoperatively vs. 3 months (N, Mean, SD, Median, Min., Max, 95% CI.) by OVD groups | | | Sensitivity/SF/PP |
| SECONDARY SAFETY ENDPOINTS | | | |
| Serious and/or device related adverse event rates (No. and percent) compared to ISO SPE rates | X | X | SF |
| Serious and/or device related adverse event rates over time (No. and percent) | | | |
| Grades of inflammation (No. and percent) over time and cumulatively (epithelial and stromal edema, cells and flare, anterior and posterior synechiae, fibrin presence) | X | X | SF |
| IOP 30mmHG spike rate (No. and percent, 95% CI) between OVD groups at 6 hour, 1 day, 1 week, 1 month and 3 months postoperatively | X | X | SF |
| Change of IOP from baseline at 6-hour, 1-day, 1-week, 1-month, and 3-month postoperatively between OVD groups (N, Mean, SD, Median, Min, Max.) | X | X | SF |
| ADDITIONAL ENDPOINTS | | | |
| Non-directed ocular visual symptoms (No. and percent) over time and cumulatively | X | X | SF |
| Other AE (non-serious, non-device related)/Medical findings (No. and percent) over time and cumulatively | X | X | SF |
| Monocular BCDVA by acuity line over time (No. and percent) | X | X | SF |
| Percent 20/40 or better vs. ISO SPE rate | | | |
| Monocular UCDVA by acuity line at 1 day (No. and percent) | X | X | SF |
| Other IOP/ECC Tables | | | |
| IOP at preoperative, 6 hour, 1 day, 1 week, 1 month and 3 month (N, Mean, SD, Median, Min., Max) | X | X | SF |
| ECC at preoperative, 3 months and difference between preoperatively vs. 3 months (N, Mean, SD, Median, Min., Max) | X | X | SF |
| Other Adverse Event Tables | | | |
| Non-adverse event/procedures (No. and Percent) | X | X | SF |
| Listing of serious and/or device-related Adverse Events by event and by OVD type (include site, age, last reported BCDVA, complications) | X | X | SF |
| | | | |

KEY:OVD=viscoelastic used, VA=Visual acuity, UCDVA=Uncorrected distance visual acuity, BCDVA=Best corrected distance visual acuity, ITT=Intent to Treat, PP=Per protocol, SF=Safety, SD=Standard deviation, Min.=Minimum value, Max.=Maximum value, C.I.=Confidence interval, X=Tables will be provided – blank indicates table will not be generated for that group, 3M=3-month postoperative visit

TIME FRAME: The 3-month postoperative visit is the key timeframe for reporting.

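### SAP 2.1 defines the best-case imputation by the same rule as the worst case, so the bound favourable to the test OVD is missing for both primary endpoints

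*SAP*

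**What the plan says.** SAP section 2.1, under Sensitivity Analysis, covers all randomized subjects, whatever OVD was used. It states that "different imputation approaches (e.g. worst-case scenario, best-case scenario and tipping point) will be used" for missing data. For the between-eye difference it specifies that "a worst-case scenario will be performed with the worst difference score (that favoring the control the most) assigned to the missing data". The next sentence reads: "For the best-case scenario, the difference score favoring the control OVD the most will be assigned to missing data". A tipping-point analysis is added only if more than 10% of randomized subjects lack data at the primary time point.

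The protocol names the scenarios without defining them. The Synopsis says "Per-protocol and sensitivity analyses (e.g., worst-case, best-case and tipping-point analyses) will also be provided for the primary endpoints", and section 20.1 repeats that "sensitivity analyses (e.g., worst-case, best-case and tipping-point analysis) will also be provided for the primary IOP and ECC endpoints".

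The direction of each difference is fixed in SAP sections 5.1 and 5.2: control minus test for the spike rate (margin -10%) and test minus control for percent ECC change (margin -5%). In both, a negative value is unfavourable to the test OVD. SAP Appendix I lists the sensitivity population for "Cumulative IOP 30mmHg spike rate (95% CI.) between OVD groups" and for "Mean difference between OVD groups in percent ECC change preoperatively vs. 3 months".

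**The concern.** Worst-case and best-case imputation are meant to bracket the result: one end as bad for the test product as the missing data allow, the other as good. Here both ends carry the same rule. The SAP itself calls the control-favouring score the worst one, so the same score cannot also define the best case.

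If the rule is followed, the reader of the sensitivity tables sees one number under two opposite labels, and the uncertainty due to missing data appears on one side only. If it is not followed, a programmer has replaced the written rule by a guess. A correction made after unmasking would move a sensitivity result in favour of the test product and would be open to the charge of being post hoc. Made now, it is neutral.

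**Working it through.** The plan gives no figure for this point, so there is none to reproduce. The rules are set side by side first; the arithmetic then illustrates size.

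**The rules**

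| Endpoint (direction) | Worst case as written | Best case as written | Best case as the label implies |
|---|---|---|---|
| IOP spike (control minus test) | most negative | most negative | most positive |
| Percent ECC change (test minus control) | most negative | most negative | most positive |

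Neither the rest of the SAP nor the protocol supplies another best-case rule.

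**IOP spikes**

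Inputs: spike rate 0.30 and between-eye correlation 0.5 (SAP section 8); about 230 operated and 200 evaluable subjects (protocol sections 8 and 10.1). Assumptions: no observed difference, and missing pairs wholly missing.

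- Each pair scores -1, 0 or +1. Discordance = 2 × 0.30 × 0.70 × (1 - 0.5) = 0.21, or 42 of 200 pairs, 21 in each direction.
- Missing pairs: 230 - 200 = 30 (13.0%).
- Assigning -1 to all 30: mean = -30/230 = -13.0 points.
- Variance = (42 + 30)/230 - 0.1304² = 0.296. SE = √(0.296/230) = 3.59 points.
- 95% CI = -13.0 ± 1.96 × 3.59, that is -20.1 to -6.0.
- Assigning +1 instead: +13.0, 95% CI 6.0 to 20.1.

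The same formulas with less missing data:

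| Wholly missing | Both scenarios as written (95% CI) | Corrected best case (95% CI) |
|---|---|---|
| 30 of 230 (13.0%) | -13.0 (-20.1 to -6.0) | +13.0 (6.0 to 20.1) |
| 10 of 210 (4.8%) | -4.8 (-11.5 to 2.0) | +4.8 (-2.0 to 11.5) |
| 10 of 230 (4.3%) | -4.3 (-10.7 to 2.0) | +4.3 (-2.0 to 10.7) |

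In the two rows with 10 missing pairs, missingness is below the 10% trigger, so no tipping-point analysis is required. The result labelled best case would still have a lower limit beyond -10, while the corrected one stays inside the margin.

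**Percent ECC change**

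Inputs: SD 12% and correlation 0.5 (SAP section 8). The SAP does not say what the extreme score is, so a value must be assumed.

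- SD of the paired difference = √(2 × 12² × (1 - 0.5)) = 12.0 points.
- Taking the score as the most extreme of 200 normally distributed differences gives about 2.75 SD = 33.0 points.
- Shift = 30 × 33.0/230 = 4.30 points.
- Variance after imputation = (199 × 144 + 30 × 33.0² - 230 × 4.30²)/229 ≈ 249. SE = √(249/230) ≈ 1.04. The 95% half-width is 1.97 × 1.04 ≈ 2.05.

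| Assumed extreme score | Both scenarios as written (lower 95% limit) | Corrected best case (lower 95% limit) |
|---|---|---|
| 24 points (2 SD) | -3.13 (-4.92) | +3.13 (+1.34) |
| 33 points | -4.30 (-6.36) | +4.30 (+2.25) |
| 36 points (3 SD) | -4.70 (-6.84) | +4.70 (+2.55) |

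The margin is -5 points.

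**The case against.** The strongest reply is that this is an obvious drafting slip with no bearing on any decision. The labels and the description of the approaches as different make the intended meaning plain, and a careful programmer would query the sentence. Success on both primary endpoints rests on the ITT multiple-imputation analysis. For non-inferiority the stress test that matters is the worst case, which is correctly specified. Appendix I lists a sensitivity population but names no separate best-case table.

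Most of that stands, and it limits the severity. It does not make the rule right: this is operative SAP text for a named analysis of both primary endpoints, and nothing else corrects it.

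The sizes can also be called extreme, and that is fair. SAP section 8 states that "Cumulative IOP spikes are defined as an IOP of 30 mm Hg or greater at any visit". A subject who misses the 3-month visit may already have earlier IOP readings, and a spike already recorded in an eye cannot be undone. Few subjects operated in both eyes would be wholly missing. The sensitivity set is all randomized subjects, for which 230 is only a stand-in. The ECC values depend on an assumed score.

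Finally, at 13% missing the tipping-point analysis would be triggered. It is conditional, however, and is not defined as the bound favourable to the test OVD, so it does not replace the best case.

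**Conclusion.** The concern holds. As written, the worst and best cases are the same imputation, the range between them has zero width, and the bound favourable to the test OVD is not specified for either primary endpoint. That conclusion comes from the text alone and needs no assumption.

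The sizes above are illustrations. They assume no observed difference, wholly missing pairs and the planning values of SAP section 8, plus normality and an assumed extreme score for ECC. The IOP values are upper limits.

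The consequence is limited to sensitivity reporting. The primary analysis, type I error, sample size and adverse bound are unaffected, and the error is conservative. It should be fixed, but it does not threaten the primary conclusion.

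**What to change.** In the best-case sentence of SAP section 2.1, replace control by test, so that missing differences receive the score most favourable to the test OVD. This is a one-word correction. It needs no new data and no added analysis, and it should be made before programming and while the study is still masked.

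It would be sensible to state in the same edit what the extreme score is for each endpoint, and how pairs with some observed IOP visits are handled. For ECC the assumed score alone moves the worst-case lower limit from -4.92 to -6.84, across the -5 margin. This costs a sentence or two.
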